## **9 STUDY OVERSIGHT**

The overall study principal investigators (PIs) along with the principal investigator (Program Lead) at CRO will be responsible for this real-world study oversight, including monitoring safety, ensuring that the study is conducted according to the protocol and ensuring data integrity. The Program Lead within the CRO will review the data for safety concerns and data trends at regular intervals, and will promptly report to the study PIs, the central IRB (and any local IRBs, if applicable) and to the study Sponsor any ADRs, protocol deviation, or any other significant event that arises during the conduct of the study.

## **10 SITE MONITORING, QUALITY CONTROL AND ASSURANCE**

Study site monitoring is conducted to ensure that the rights of human Subjects are protected, that the study is implemented in accordance with the protocol and/or other operating procedures, and that the quality and integrity of study data and data collection methods are maintained. Site monitoring for this minimal-risk, real-world study will be performed by the CRO. The CRO will

---

routinely evaluate study processes and documentation based on the protocol and other applicable requirements, if any.

All site monitoring activities will be performed remotely for this study, with occasional visits to select sites to check on study procedures. Site Investigators or the assigned study coordinators will be contacted routinely by phone and email to ensure that study procedures are followed per protocol and study subject follow-ups happen as planned. Study data review will be undertaken by the CRO staff following the baseline and follow-up encounters for data collection from Site Investigators and study Subjects. Data inquiries will be shared with the Site Investigators for clarification and/or fill missing data elements, or gather additional information, as it may pertain to reported AEs/SAEs.

## 11 DATA MANAGEMENT

The study data portal will comprise of two distinct, linked data sources, one being the traditional EDC containing eDCF to gather data from Site Investigators; another being the mobile App that gathers data directly from study Subjects. The back-end EDC platform will be programmed with edit checks to ensure that the incoming data from Site Investigators and Subjects are routinely checked for data quality, any systematic missing data, trends in select outcome measures and safety events.

A centralized data review strategy will ensure consistency, integrity, logical completeness, and coding of collected data. Queries will be generated for study sites to solicit additional required information, as needed. Any necessary data corrections in the EDC portal at the back-end will be made by the central research staff, and ratified by the CRO Program Lead for appropriateness and correctness.

Incoming AE data will be routinely checked to flag SAEs and other pertinent high-priority safety events, gather additional information from the sites (as/if needed), and additionally collected information will be integrated back with the master study dataset, while the safety data is processed for expedited reporting to study sponsor.

Any additional quality assessment(s) will be carried out for the study per the study specific data management plan. Following completion of all data review activities for all patients, records within the master dataset will be locked, followed by completion of medical coding for concomitant medications and adverse events and preparation of dataset for statistical analyses.

## 12 STATISTICAL CONSIDERATIONS

Detailed plans for the statistical methods will be provided in a Statistical Analysis Plan (SAP) which will be finalized prior to database lock.

### 12.1 Sample Size Considerations

No formal sample size and power calculations were undertaken. Considering the descriptive nature of the study and the feasibility of recruiting the study population, approximately 300 study Subjects from across a maximum of 50 clinical sites for the entire study has been identified as a sample to guide the planned analysis addressing the study objectives.

### 12.2 Analysis Populations and Datasets

Statistical analysis and data tabulation will be performed using the following analysis populations unless specified otherwise:

- Safety Population: All patients who received at least one dose of sarecycline during the study observation period, as part of usual care.
- Full Analysis Set (FAS): All patients within the Safety Population that had at least some data pertaining to study primary research objective.

There is a likelihood that the Safety population and FAS may be the same in certain scenarios, including when no patient discontinues sarecycline following study enrollment and prior to 3-month follow-up data collection. In such scenarios, FAS will be the main dataset for all analyses. In the event that the safety population and FAS differ, all safety evaluations (part of additional

objectives) will be conducted among the safety population, while FAS will be used to conduct analyses addressing rest of the study objectives, including the primary objective.

## 12.3 General Statistical Procedures

### 12.3.1 Overview

Data from Site Investigators and study Subjects will be combined into one dataset. No site-specific analyses will be conducted. Validated instruments will be scored according to developer guidelines, reporting domain scores and overall summary scores, as appropriate. Home-grown questions/items will be analyzed and reported individually, based on the respective response scales.

Statistical differences in discrete variables will be assessed using a  $\chi^2$  test. Continuous measures will be assessed using the appropriate parametric or nonparametric test. P values  $\leq 0.05$  will be considered significant in all analyses. All statistical analyses will be based on all available data assuming that all missing data are uninformative and will be conducted using appropriate statistical software, such as SAS.

The final study analyses will be conducted after the completion of 12 weeks of data collection for all study Subjects.

### 12.3.1 Summary Statistics

The descriptive statistics for all the continuous variables will include the mean, median, 25th percentile, 75th percentile, standard deviation (SD), standard error of mean (SEM), minimum, maximum, and number of Subjects. Descriptive summaries will be provided for raw, CFB, and %CFB values for relevant endpoints, where applicable. Frequency distributions for all the categorical variables will be presented as counts and percentages. Summaries will be provided by encounters, as appropriate. Results from the descriptive analyses will be presented as summary tables and figures.

### **12.3.2 Subgroup Analysis**

Primary and additional outcome measures may be summarized and repeated for the following subgroups, only if sample size allows by study visit using FAS:

- Gender: male and female
- Age groups: 9 to 17 years and  $\geq 18$  years
- Race: white, African-American/Black, other
- Body mass index:  $< 25 \text{ kg/m}^2$  and  $\geq 25 \text{ kg/m}^2$
- Baseline facial IGA score: moderate and severe
- Oral contraceptive use in females: female Subjects who use oral contraceptives versus female Subjects who do not (if sample size permits)

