## 6.3 General Statistical Procedures

### 6.3.1 Overview

Data from Site Investigators and study Subjects will be treated separately, and combined into one dataset, based on the study assessments of interest. Validated instruments will be scored according to developer guidelines, reporting domain scores and overall summary scores, as appropriate. Home-grown questions/items will be analyzed and reported individually, based on the respective response scales. Change from Baseline (CFB) in scores (for continuous variables) or proportions (for discrete variables) will be computed as Week-12 minus Baseline measure for respective question responses.

Discrete measures will be assessed using summary statistics encompassing percentage of Subjects reporting particular outcome measures. The statistical differences in discrete variables to compare different patient groups (for subgroup analysis) for a given measure at a particular timepoint (such as Baseline or Week-12), or CFB in proportion of patients reporting a particular response to an outcome measure at a particular timepoint (such as Week-12) will be assessed using a  $\chi^2$  test. In case of likert scales, to compute P-values for CFB in proportions, the top-two response categories (of a likert scale) for a given question at Baseline will be grouped together into a single group proportion (versus the rest of the population/responders all together) and compared to the same group proportion at Week-12; the procedure will be repeated for the bottom-two response categories (of a likert scale) for a given question, by grouping them together into a single group proportion and compare it to the same group proportion at Week-12. For example, for ASIS item # 1 (how oily is your face right now), proportion of patients reporting “Not at all/A little” at Baseline will be grouped together (vs. rest of the population/responders) and compared to proportion of patients reporting “Not at all/A little” at Week-12; similarly, proportion of patients reporting “Quite a bit/Very” at Baseline will be grouped together and compared to proportion of

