patients reporting “Quite a bit/Very” at Week-12, to compute respective P values. Continuous measures will be assessed using summary statistics; paired sample t-tests will be used to assess statistical differences for CFB evaluations, while independent sample t-tests will be used to assess statistical differences between different patient groups (for subgroup analysis) for a given measure at a particular timepoint (such as Baseline or Week-12).

Computation of statistical differences will be performed only as an exploratory step (and not for hypothesis testing), considering the descriptive nature of the study; for such exploratory evaluation, P value  $\leq 0.05$  will be considered significant. All statistical analyses will be based on all available data assuming that all missing data are uninformative and will be conducted using appropriate statistical software, such as SAS.

An interim analysis will be conducted using FAS, upon completion of 12 weeks of data collection (from both patients and clinicians) for ~200 study Subjects, using the statistical methods identical to the analyses planned for FAS-based final data analyses; the focus of the interim analyses will be the primary objective, secondary objective and select additional objectives, as outlined below; no subgroup analyses will be considered.

- FAS cohort demographics
- PROs: Antibiotic attitudes at baseline
- PROs: CFB in EPQ measures
- PROs: CFB in ASIS measures
- PROs: CFB in Patient Acne Severity and How Face Looks (with and without LOCF imputation)
- PROs: CFB in Parent/caregiver concerns about the child with Acne:
  - Understanding child's concerns
  - Concerned about child's acne
  - Concerned about child's ability to accomplish future goals
- Facial IGA and Facial IGA success (with and without LOCF imputation)
- Select comparison of patient and clinician reported measures: Acne Severity (with LOCF imputation)

- Select comparison of pediatric patient and caregiver reported measures:
  - Understanding child's concerns
  - Concerned about child's acne
  - Concerned about child's ability to accomplish future goals
- Clinician satisfaction with sarecycline
- Sarecycline treatment characteristics

The description of the individual study measures are outlined in the forthcoming sections.

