### **6.3.2 *Subgroup Analysis***

Primary and select additional outcome measures (as individually identified in the following sections) will be summarized and repeated for the following subgroups, using FAS:

- Gender: male and female
- Age groups: 9 to 17 years and  $\geq 18$  years
- Race: white, african-american/black, other

- Body mass index: < 25 kg/m^2 and ≥ 25 kg/m^2
- Baseline facial IGA score: moderate and severe
- Concomitant use of contraceptives in females: yes and no

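### The SAP drops the protocol's sample-size condition on subgroups and tests every discrete subgroup comparison by chi-square with no small-cell rule, so sparse rows can carry a misleading significant label (minor)

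*Protocol*

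**What the plan says.** - **Protocol 12.3.2** makes subgroup summaries optional and conditional: outcomes "may be summarized and repeated for the following subgroups, only if sample size allows by study visit using FAS". It repeats the condition for oral contraceptive use.
- **SAP 6.3.2** makes them firm: outcomes "will be summarized and repeated for the following subgroups, using FAS". No size condition remains, for contraceptives or anything else.
- **SAP 6.3.1** sets the test. "The statistical differences in discrete variables to compare different patient groups (for subgroup analysis) for a given measure at a particular timepoint", it says, "will be assessed using a $\chi^2$ test". It names no exact test, continuity correction or minimum count. Protocol 12.3.1 has the same general rule ("Statistical differences in discrete variables will be assessed using a" chi-square test).
- **For continuous measures**, SAP 6.3.1 says that "independent sample t-tests will be used to assess statistical differences between different patient groups (for subgroup analysis"). This covers the ASIS domain scores in Table 7.1.11.
- **Threshold**, SAP 6.3.1: "for such exploratory evaluation, P value $\leq 0.05$ will be considered significant". The same sentence describes the tests as exploratory and not hypothesis tests.
- **Age groups.** Both subgroup lists give two, 9–17 and 18 or over. The SAP shells print three rows, with 9–11 on its own, and ask for a p-value (for example Tables 7.1.7.1, 7.1.16.1 and 7.2.4.8).

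**The concern.** The protocol's condition was the only safeguard against testing rows too small to test. The SAP removes it, while its shells split age more finely than its text does. Chi-square p-values rely on a large-sample approximation. With an expected count well below 1 in one cell, a single patient can move the statistic past its critical value. The table would then show a subgroup difference as significant when the exact probability does not support it.

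Nothing else in the plan guarantees workable rows. SAP 6.1 has no sample-size calculation. SAP 6.2 restricts the full analysis set to patients who completed the Week 12 survey, so rows shrink with attrition.

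**Working it through.** The documents give no subgroup sizes or response rates, so there is no planned figure to reproduce.

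**Inputs.** From the documents: about 300 enrolled, a full analysis set of Week 12 completers, the chi-square test, and the 0.05 threshold. Assumed: a full analysis set of 250, with 100 aged 12–17, a 9–11 row of r patients, and 150−r adults. Both r and the response rate are varied.

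**1. One example in full.** Responders are 1/5, 2/100 and 3/145. The overall rate is 6/250 = 0.024, so expected responders are 0.12, 2.40 and 3.48. Each row contributes (O−E)² / [E(1−0.024)]:
- 9–11: 0.88² / (0.12×0.976) = 6.61
- 12–17: 0.40² / (2.40×0.976) = 0.07
- adults: 0.48² / (3.48×0.976) = 0.07

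The total is 6.75 on 2 df, p=0.034. The Fisher-Freeman-Halton exact p is 0.19. Almost all of the statistic comes from one child.

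A second table, 1/3, 2/100 and 3/147, has a smallest expected count of 0.07. It gives chi-square 12.40, p=0.002, against exact p=0.074.

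**2. How rare the response must be.** If a one-patient row holds a responder and the other rows share rate p, the statistic is about (1−p)/p. It passes the 2-df critical value of 5.99 when p is below 1/6.99 = 14.3%. By symmetry, a lone non-responder does so when p is above 85.7%. Larger rows need a more extreme rate. With 300 patients split 40/60 between 12–17 and adults outside the 9–11 row, one responder in a row of 2 gives p=0.019 at 5% but 0.10 at 8%. One in a row of 5 gives 0.029 at 2% but 0.11 at 3%.

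**3. True error rate of the nominal 5% test.** All 3×2 tables were enumerated under a common response rate, and the probabilities of those with a chi-square statistic of at least 5.99 were summed.

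| 9–11 row | 2% | 5% | 10% | 20% | 50% | 90% |
|---|---|---|---|---|---|---|
| 1 | 0.030 | 0.063 | 0.112 | 0.049 | 0.026 | 0.112 |
| 2 | 0.049 | 0.101 | 0.050 | 0.060 | 0.031 | 0.050 |
| 3 | 0.068 | 0.085 | 0.050 | 0.046 | 0.035 | 0.050 |
| 5 | 0.081 | 0.051 | 0.055 | 0.049 | 0.046 | 0.055 |
| 8 | 0.075 | 0.058 | 0.051 | 0.047 | 0.047 | 0.051 |
| 10 | 0.058 | 0.055 | 0.051 | 0.047 | 0.049 | 0.051 |
| 12 | 0.055 | 0.052 | 0.049 | 0.047 | 0.049 | 0.049 |

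The inflation sits in a few cells: very small rows with a rare or near-universal response. Over rows of 2 to 12 and these rates, the exact test stays between 0.034 and 0.049.

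**4. How many p-values.** The shells ask for 11 EPQ tables × 2 visits × 6 factors = 132. Tables 7.1.16.1, 7.1.16.2 and 7.2.4.5 add 3 × 24 = 72, and Tables 7.2.4.8 and 7.2.9 add 2 × 6 = 12. The total is 216, of which 36 are for age and 36 for race. Eight have nothing to test:
- The 6 baseline p-values in Table 7.2.4.5. Eligibility requires IGA 3 or 4, so no one is clear or almost clear.
- The 2 age p-values for EPQ10. SAP 5.4 says that question was put to ages 12–17 only.

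That leaves 208, of which 33 are for age.

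**5. Is an exact test enough alone?** No. With 250 patients, 1/1 against 3/100 and 4/149 gives exact p=0.040. A minimum row size is also needed.

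**The case against.** The case for leaving this alone has four parts.

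- **The p-values are exploratory.** SAP 6.3.1 says so, and the primary analysis is descriptive. This stands, and it limits the consequence. It does not remove the significant label, which the same sentence attaches.
- **Ages 9–11 are not a listed subgroup.** If the shells followed SAP 6.3.2, the age example would disappear. This also stands, so part of the defect is a mismatch between shells and text. The three race rows are in the listed subgroups, and the arithmetic depends only on row sizes. The documents do not say whether any race row is that small.
- **The added error is small.** With no true differences, 208 valid tests would give about 208×0.05 = 10.4 false positives. If all 33 age tests ran at the worst rate found for rows of 2 to 12, the excess would be 33×(0.101−0.05) = 1.7. In many scenarios chi-square is at or below 0.05. This stands.
- **A row-size rule does most of the work.** At 10 patients the error rate is already 0.047 to 0.058, so an exact-test rule adds little for that row. It still covers rare responses in other small tables.

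A reader might infer that every subgroup comparison is affected. The t-test for ASIS domain scores rules that out. A reader might also infer that one child's favourable answer could create a false finding in IGA success or investigator satisfaction. The documents do not support that, because they give neither the Week 12 rates nor the row sizes. Under the 250-patient assumption, one responder in a row of 2 gives p=0.18 at a 10% rate and 0.58 at 20%. If satisfaction is high, one favourable answer in a one-patient row gives p=0.81 to 0.95 at rates of 70 to 90%.

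**Conclusion.** The point holds in limited form, and it is minor. The SAP removes the protocol's condition, keeps chi-square with no small-cell rule for discrete comparisons, and adds a potentially sparse age row in the shells.

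Under the assumed 250 patients, the true error rate reaches about 0.08 to 0.10 for particular rows of 2 to 5 patients at rates of 2 to 5%, and 0.11 for a one-patient row at 10% or 90%. It is close to 0.05 once the row holds 10 or more. The number aged 9–11 is unknown, so whether the problem arises in practice is also unknown.

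The clearest candidate is patient-rated clear or almost clear at baseline (Table 7.1.16.1). Every patient enters with investigator-rated moderate or severe acne, so that response is likely, though not certain, to be rare. The harm is a misleading significant label, not a wrong trial decision.

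**What to change.** - **SAP 6.3.2:** restore the protocol's condition with a number. For example, rows with fewer than 10 patients show n (%) only and are left out of the p-value. The protocol gives no threshold; 10 is suggested by the table of error rates.
- **SAP 6.3.1:** for discrete subgroup comparisons, use Fisher's exact test (Fisher-Freeman-Halton for three rows) when expected counts are small, for example any below 5, and chi-square otherwise.
- **Shells, age rows:** align them with SAP 6.3.2. Most shells also print the third row as 12 years and over, which overlaps the 12–17 row; Tables 7.1.11 and 7.1.16.1 print 18 and over.
- **Shells, p-values:** remove those that cannot be computed, namely baseline IGA in Table 7.2.4.5 and age for EPQ10.

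The cost is two sentences in the SAP, a program option and shell edits. The exact test is slightly conservative, and a few p-values will be blank.

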### **12.3.3 Multivariate Analyses**

CFB in key study outcome measures at Week 12 post-index date, and at Weeks 4 and 8 (if applicable) post-index date will be assessed using relevant multivariate analyses, adjusting for subject baseline characteristics and other variables (such as medication adherence) to discern the factors influencing these outcomes, as feasible. Repeated measures analyses with covariates may be used to statistically test the changes/trends for relevant outcome measures over time.

Pearson correlation coefficients may be used to assess the correlation between key outcome measures; this may also inform the consideration of covariates in select multivariate analyses (to reduce multicollinearity).

## **12.4 Primary Endpoint Analysis**

The primary endpoint of PROs at Week 12 will be assessed descriptively, using the FAS dataset.

For ASIS questionnaire, the individual item and domain/subscale scores will be created per instrument developer instructions, analyzed descriptively for the baseline and Week 12 encounters,

---

treating the responses as categorical variables and/or continuous variable, as appropriate. For the overall questionnaire data evaluation, no missing data imputation will be applied to compute domain/subscale scores.

The Patient Global Assessment (PtGA) of acne severity based on the single ASIS item (# 9) will be analyzed separately using descriptive statistics and reported for Week 12. Specifically, proportion of Subjects who reported clear (0) and almost clear (1) on the item scale at Week 12 will be assessed. Last Observation Carried Forward (LOCF) data imputation method will be used to impute responses to ASIS item # 9 at Week 12 for the Subjects with missing data at Week 12.

Patient self-rating of their appearance based on the single ASIS Item (# 10) will be analyzed separately using descriptive statistics and reported for Week 12. Specifically, proportion of Subjects reporting "very good" or "excellent" at Week 12 will be assessed. LOCF data imputation method will be used to impute responses to ASIS item # 10 at Week 12 for the Subjects with missing data at Week 12.

For Expert Panel Questionnaire, the items will be analyzed individually, using descriptive statistics and reported for Week 12.

For all PRO elements, descriptive statistics will be computed, stratified by age and other relevant subgroups, to explore the relationship between these HRQoL items and subject characteristics.

## 12.5 Secondary Endpoint Analysis

The secondary endpoint of the study is the proportion of patients with Facial IGA success at Week 12, defined as a 2-point decrease in IGA score from baseline and a score of 0 (clear) or 1 (almost clear). The analyses of IGA success will be conducted for the overall cohort (using FAS), as well as stratified by age and other relevant subgroups. Relationship between this endpoint and subject characteristics will be explored using descriptive analyses. LOCF data imputation method will be used to impute responses at Week 12 for the Subjects with missing data at Week 12.

